### 5.3 Multiple Comparisons and Multiplicity

This is a proof of concept study for which no formal statistical hypotheses were defined. When presented, nominal p-values will not be interpreted inferentially. The results of the study will be interpreted by the overall pattern of benefits of opaganib.

### 5.4 Handling Withdrawals and Missing Data

Missing data in the primary endpoint are handled as described in sections 3.2.1 and 7.2. Sections 3.2.2 and 7.3 provides details on handling missing data for the secondary efficacy endpoints. Generally, no imputation will be performed for safety endpoints unless stated otherwise in the specific endpoint analysis. For time to event analysis, early withdrawal (or death before event of interest) will be addressed via right censoring, as described in Sections 3.2.2.

### 5.5 Study days and visit windows

The study data will be summarized as collected at the scheduled study day during DB and follow-up phases. In case assessments are done at the Early Termination visit, these assessments will be used as data for the scheduled assessment day closest to the early termination time point, in case the corresponding data are missing from this assessment day.

### 5.6 Subgroups

The subgroup of low-flow vs. high-flow oxygen will be define based on the baseline oxygen required type. Subject will be classified with 'High-Flow' if baseline oxygen

required was positive pressure or high flow nasal cannulas and 'Low-Flow' if baseline oxygen required was regular.

### **6 STUDY POPULATION**

## 6.1 General

Study population summaries will be presented by treatment group and overall unless otherwise noted.

# 6.2 Patient Disposition

The subject disposition will be summarized as follows and presented for each treatment group and overall, unless otherwise specified. Summary will include all screened subjects. The percentages will be calculated from the ITT population, unless otherwise specified.

- The number of all screened subjects (i.e. the number of subjects in the Screened population), presented only for overall group
- The number (%) of subjects who were not eligible for the study (% calculated from the Screened population), including the distribution of reasons for not eligible for the study, presented only for overall group
- The number (%) of subjects screened but not randomized, if applicable (% calculated from the Screened population), presented only for overall group
- The number of randomized subjects (i.e. the number of subjects in the ITT population)
- The number (%) of randomized but not treated subjects, if applicable
- The number (%) of subjects in the Safety population (i.e. treated subjects)
- The number (%) of subjects in the mITT population
- The number (%) of subjects who completed the study treatment according to protocol (i.e. on day 14 or on day 10 if discharged from the hospital without requiring supplemental oxygen before day 14)
- The number (%) of subjects who discontinued the study treatment prematurely, including the distribution of reasons for premature discontinuation
- The number (%) of subjects who completed the study
- The number (%) of subjects who discontinued the study prematurely, including the distribution of reasons for premature discontinuation

# 6.3 Demographics and Baseline Characteristics

Demographics and baseline characteristics will be summarized by treatment group and overall using ITT, mITT and Safety populations. Summaries will be presented with the appropriate descriptive statistics as specified in section 5.1 above.

The following will be provided:

- Demographics:
  - Age (years) (continuous)
  - Gender: Male, Female (categorical)
  - Childbearing Potential: Yes, No (categorical, females only)
  - Ethnicity: Hispanic or Latino, Not Hispanic or Latino, Unknown, (categorical)

- Race: White, American Indian or Alaska native, Asian, Black or African American, Native Hawaiian or Other Pacific Islander, Other (categorical)
- Smoking status: Never, Former, Current (categorical), and packyears
- Stratification factors (categorical):
  - Age (years):  $<70, \geq 70$
  - HbA1c at screening:  $<6.5, \ge 6.50$ )
  - Oxygen requirement at baseline requiring non-invasive positive pressure ventilation (e.g. via PEEP, BIPAP, CPAP): yes or no
- Vital signs at baseline, including supplemental oxygen requirement

### 6.4 Covid-19 Disease Information

Disease information will be summarized by treatment group and overall using ITT, mITT and Safety populations. Summaries will be presented with descriptive statistics as specified in section 5.1 above

- Reason for hospitalization
- Time from onset of symptoms to Hospitalization (Days)
- Time from onset of symptoms to diagnosis (Days)
- Time from onset of symptoms to randomization (Days)
- Time from diagnosis to hospitalization (Days)
- Time from diagnosis to supplemental oxygen (Days)
- Time from diagnosis to randomization (Days)
- Time from hospitalization to supplemental oxygen (Days)

### 6.5 Medical History

Medical history data will be summarized by treatment group and overall using ITT and Safety population. All medical history terms will be coded using the Medical Dictionary for Regulatory Activities (MedDRA). The number and percentage of subjects with at least one medical history term will be summarized by System Organ Class (SOC) and by Preferred Term (PT) within SOC for each treatment group and overall. The table will be sorted by overall descending frequency of SOC and then, within a SOC, by overall descending frequency of PT.

All medical history data will be listed.

# 6.6 **Prior Medications**

Prior medications will include all recorded medications and supplements a patient was taking during the screening period that were stopped prior to administration of the study drug.

All medications will be classified using the Anatomical Therapeutic Chemical (ATC) classification codes and preferred terms (PT) from the World Health Organization Drug Dictionary (WHO-DD). Prior medications data will be summarized by treatment group and overall using ITT and Safety populations. The number and percentage of subjects with at least one medication term will be summarized by ATC Level 4 category and by PT

within an ATC Level 4 for each treatment group and overall. The table will be sorted by overall descending frequency of ATC Level 4 and then, within an ATC Level 4, by overall descending frequency of PT.

In addition, all prior medications data will be listed.

### 6.7 Electrocardiography

Electrocardiogram findings (normal, abnormal, and missing) at baseline will be summarized using appropriate descriptive statistics, and will be presented for the Safety population.

#### 6.8 Physical Examinations

Physical examination findings (normal, abnormal, and missing) at baseline will be summarized by treatment group and overall using Safety population. Summaries will be presented using appropriate descriptive statistics.

#### 6.9 Chest X-Ray

Chest X-ray findings (normal, abnormal, and missing) at baseline will be summarized by treatment group and overall using Safety population. Summaries will be presented using appropriate descriptive statistics.

#### 6.10 Protocol Violations

All protocol violations will be listed.

### 7 EFFICACY ANALYSIS

#### 7.1 General

The analysis of the primary efficacy endpoints will be performed on the mITT, ITT and safety populations, with the mITT population serving as the primary analysis population. The secondary efficacy endpoints will be analyzed using the mITT populations, unless otherwise noted for a specific endpoint.

Summaries will be presented by treatment group, unless otherwise noted.

### 7.2 Primary Efficacy Endpoint Analysis

The primary analysis will be based on the modified Intent to treat population (mITT), which consist of all patients that were randomized and treated with at least one dose of study drug,

The primary analysis will be based on the baseline-adjusted AUC calculated individually for each subject, as defined in section 3.2.1. Descriptive statistics of the baseline-adjusted AUC will be presented by group and group means will be presented along with 95% confidence interval. The difference in means between the groups will be estimated and presented with 95% confidence interval. Plots presenting individual baseline-adjusted AUC will be presented. Difference between group medians with confidence interval will also be estimated using the Hodges-Lehmann statistics and will be presented along with the non-parametric Wilcoxon rank sum test.

#### 7.2.1 Sensitivity and supportive analyses

Sensitivity and supportive analyses for the primary endpoint analysis will address the following aspects:

#### 7.2.1.1 Missing data

The primary analysis above is based on individual AUC calculation, where in case that all supplemental oxygen values are missing after discharge or early treatment discontinuation that occur while subject still requires supplemental oxygen (before day 14), the last value is carried forward - until Day 14, or death, if occurred before. In addition, worst case imputation is applied for subjects who died any time within 14 days and on days of intubation.

A sensitivity analysis to the above missing data handling approach will be performed using an AUC summary statistics approach, in which groups AUC is calculated from the estimated parameters of a Repeated-Measures model. More specifically, taking as the dependent variable the observed daily oxygen requirement per each subject (change from baseline), a model incorporating factors for group, day (categorical) and group by day interaction will allow estimation of the mean oxygen requirement at each day, for each group. The model will be implemented using the MIXED procedure in SAS software with subject taken as random factor. To confirm that correlation among observations from the same subject are adequately modeled in this MIXED model application, the following correlation structures will be fitted as well: Unspecified (UN) and Autoregressive(1)

Statistical Analysis Plan	RedHill Biopharma
Version: 3, Date: 13-DEC-2020	Study ABC-110

(AR(1)). The denominator degrees of freedom will be computed using the Kenward-Roger method. Each group mean AUC will be estimated using a linear combination of the parameter estimates after a model has been fit. Group AUCs and their difference will be presented along with 95% confidence interval.

#### 7.2.1.2 Baseline characteristics adjustment

Estimation of difference between the treatment groups when controlling for the stratification factors and baseline oxygen requirement will be performed, using regression analysis, both for the individual subjects AUC (via Analysis of Covariance) and the group AUC modeling via Repeated measures approach sensitivity analysis.

#### 7.2.1.3 Per protocol analysis

Analysis using the per-protocol population will be performed as supportive analysis.

#### 7.2.1.4 Robustness for outliers

Analysis based on ranked observations will be performed to confirm robustness of the estimated effect for potential outliers.

#### 7.3 Secondary Efficacy Endpoint analysis

This section describes the analyses to be performed on the secondary efficacy endpoints, as defined in section 3.2.2.

The secondary efficacy endpoints will be analysed using the mITT populations unless otherwise noted for a specific endpoint.

1. Time to 50% reduction from baseline in supplemental oxygen based on oxygen flow in L/min

This time to event will be analyzed as follows: Cox proportional hazards regression model will be used to estimate the hazard ratio (HR) along with 95% confidence interval, comparing Opaganib versus control group. The model will include treatment group as explanatory variable and supplemental oxygen at baseline as covariates. If possible, the stratification factors will also be included as covariates. Kaplan-Meier plot will be provided for illustration of effect (along with median estimates). Cumulative incidence function of the time to 50% reduction from baseline in supplemental oxygen will be estimated using the Kaplan-Meier estimator and will be used to estimate the 14-days cumulative incidence of 50% reduction event for each group, along with 95% confidence interval.

2. The percentage of patients no longer receiving supplemental oxygen for at least 24 hours by Day 14

This binary endpoint ("success"/"failure") will be analyzed as follows: the number of subjects with "success" and "failure" will be summarized using counts and percentages for each group. A 95% confidence interval will be constructed for the proportion of event of interest ("success") in each group. Difference in proportions will be estimated and presented along with 95% confidence interval. Exact confidence intervals will be used as needed (otherwise Wilson (Score) limits will be used). In case loss to follow-up before

event will be recorded, the Cumulative Incidence probabilities at 14-days from the starting of treatment will be estimated using time to event analysis (Kaplan-Meier estimator), censoring loss-to follow up patients at last valid observation date. This analysis will censor death on Day 14.

3. The time to two consecutive negative swabs for SARS-CoV-2 by PCR, at least 24 hours apart

This time to event endpoint will be analyzed using the same methods specified for the first secondary efficacy endpoint (without adjustment for the supplemental oxygen at baseline).

4. The time to two consecutive negative swabs for SARS-CoV-2 by PCR, at least 24 hours apart, followed by continued negative swabs

This time to event endpoint will be analyzed using the same methods specified for the first secondary efficacy endpoint (without adjustment for the supplemental oxygen at baseline).

5. The percentage of patients requiring intubation and mechanical ventilation

This binary endpoint will be analyzed using the same methods specified for the second secondary efficacy endpoint. The event of interest is defined as "Failure". As defined in section 3.2.2. death will be analyzed as "Failure".

The percentage of patients requiring intubation and mechanical ventilation by Day 14 will be analyzed similarly.

6. The time to intubation and mechanical ventilation.

This time to event endpoint will be analyzed using the same methods specified for the 1st secondary efficacy endpoint (without adjustment for the supplemental oxygen at baseline).

 The percentage of patients with at least one measurement of fever at baseline (defined as temperature >38.0 C[100.4 F]), who are afebrile (defined as temperature <37.2C [99 F]) at Day 14

This binary endpoint will be analyzed using the same methods specified for the second secondary efficacy endpoint. This analysis will be based on observed case analysis using patients with Day 14 measurement.

8. Mortality due to any cause at Day 30.

This binary endpoint will be analyzed using the same methods specified for the second secondary efficacy endpoint. The event of interest is defined as "Failure". To note, in case that loss to follow up, the associated time to event analysis to derive the 30-days mortality rate will not encounter any competing event. Kaplan Meier curves of time to death through Day 30 will also be provided.

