# 3.4 Randomization and Blinding

A total of 40 subjects 18 to 80 years old, inclusive will be randomized, using a 1:1 assignment ratio, to treatment with either Opaganib 500 mg Q12 hour (20 subjects) or Placebo (20 subjects), respectively.

A dynamic randomization using the minimization method will be used in this study by Bioforum's DM vendor. Three stratification factors will be used for the minimization algorithm:

- 1. Age at screening,  $\geq 70$  years of age, (yes or no)
- 2. HbA1c at screening,  $\geq 6.5$ , (yes or no);
- 3. Oxygen requirement at baseline, requiring non-invasive positive pressure ventilation (e.g. via PEEP, BIPAP, CPAP, HFNC), (yes or no)

The minimization algorithm will be programmed by Bioforum Ltd using Viedoc system and will employ the Pocock and Simon (Pocock S.J. and Simon R. 1975) methodology with biased coin probability of 0.8 and 'Range' as the variation method. All stratification factors will use the same weight of importance. If the subject meets the eligibility criteria, he or she will be allocated to Opaganib 500 mg Q12 hour or Placebo at 1:1 ratio respectively. Once the enrollment of the subject is approved, the investigator will assign the subject an ID number (subject number) provided by the Viedoc system after running the algorithm on the subject's stratification information.

Treatment assignments will remain blinded to the patient, investigator and hospital staff, as well as the sponsor.

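### Endpoint 2 (off oxygen by Day 14) gets only a crude risk difference, although the SAP adjusts the AUC and endpoint 1 for baseline oxygen; a supportive adjusted difference should be added

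*SAP*

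**What the plan says.** SAP 7.3 gives endpoint 2 counts, percentages, an interval for each arm and a between-arm contrast: "Difference in proportions will be estimated and presented along with 95% confidence interval". On the interval method it says: "Exact confidence intervals will be used as needed (otherwise Wilson (Score) limits will be used". No covariate is named. If patients are lost to follow-up, a Kaplan-Meier estimate at 14 days is used, also without covariates. Endpoints 5, 7 and 8 inherit this approach: "This binary endpoint will be analyzed using the same methods specified for the second secondary efficacy endpoint".

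Elsewhere the SAP does adjust:

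- Primary AUC (SAP 7.2.1.2): "Estimation of difference between the treatment groups when controlling for the stratification factors and baseline oxygen requirement will be performed, using regression analysis". This covers the AUC analyses only.
- Endpoint 1, time to 50% reduction in oxygen (SAP 7.3, Cox model): "The model will include treatment group as explanatory variable and supplemental oxygen at baseline as covariates". It continues: "If possible, the stratification factors will also be included as covariates".
- Endpoints 3, 4 and 6 use the same Cox approach, but "without adjustment for the supplemental oxygen at baseline".

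On allocation, SAP 3.4 says: "Three stratification factors will be used for the minimization algorithm". They are age 70 or over, HbA1c 6.5 or over, and a yes/no factor for the type of oxygen support. Flow in L/min is not among them.

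**The concern.** Endpoint 2 describes the same oxygen course as the AUC and endpoint 1, reduced to yes or no. A patient who starts on low flow is plausibly more likely to be off oxygen by Day 14 whatever the treatment. The SAP treats baseline oxygen as worth adjusting for in the other two oxygen outcomes. It gives no reason for leaving it out here.

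SAP 5.3 says the results will be read from the overall pattern of benefit, with no formal test. Point estimates and intervals therefore carry the message. A chance difference in starting flow would push several oxygen-related endpoints the same way, and endpoint 2 would have no adjusted figure to set against it. If adjustment is considered only after an imbalance has been seen, the choice is post hoc.

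**Working it through.** **Inputs from the documents.** About 40 patients, 20 per arm, 1:1 (SAP 3.3). Pocock-Simon minimisation on three binary factors with range, equal weights and biased-coin probability 0.8 (SAP 3.4). The sample size has no statistical basis, so there is no power figure to reproduce.

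**Assumptions, none from the documents.** Baseline flow is standardised and normal. Endpoint 2 success is about 60%. The log odds ratio is 0.4, 0.8 or 1.6 per SD of flow (odds ratio about 1.5, 2.2 or 5.0). Support type is either the top 30% of the flow scale or unrelated to flow. There is no treatment effect.

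**1. Precision of the crude difference.** Half-width = 1.96 × √(2p(1−p)/20).

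- p = 0.5: 1.96 × √0.025 = 0.31
- p = 0.6: 1.96 × √0.024 = 0.30
- p = 0.2: 1.96 × √0.016 = 0.25
- p = 0.1: 1.96 × √0.009 = 0.19

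**2. How often flow is imbalanced.** With no restriction on flow, the SD of the between-arm difference is √(2/20) = 0.316 SD. The chance of exceeding 0.32 SD is then 2 × [1 − Φ(0.32/0.316)] = 0.31. If support type is the top 30% of flow, minimisation lowers the SD to about 0.23-0.24. The chance becomes 2 × [1 − Φ(0.32/0.23)] = 0.16 to 2 × [1 − Φ(0.32/0.24)] = 0.18. Simulation under the planned minimisation gave about 15-32% over both cases. The spread comes mainly from how closely support type tracks flow, which the documents do not state.

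**3. What an imbalance does to the crude difference.** Shift per SD = β × mean of p(x)(1 − p(x)) over the flow distribution, with the overall rate held at 60%.

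| Log odds ratio per SD | Shift per SD | Shift at 0.32 SD |
|---|---|---|
| 0.4 | 0.093 | 0.32 × 0.093 = 0.030 |
| 0.8 | 0.169 | 0.32 × 0.169 = 0.054 |
| 1.6 | 0.265 | 0.32 × 0.265 = 0.085 |

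That is about 3-9 points, or roughly 3/31 = 0.1 to 9/31 = 0.3 of the half-width. In simulation, adjusting for baseline oxygen alone left a shift close to zero.

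**4. Variance saved by adjusting for oxygen alone (60% success).** At a log odds ratio of 0.4 the change is −1% to +2%, in effect nothing. At 0.8 to 1.6, one set of runs gave a reduction of 6-16% when support type is the top 30% of flow and 10-23% when it is unrelated. Over all the runs the range is about 0-26%.

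**5. Rarer outcomes and larger models.** Logistic standardisation under minimisation, support type taken as the top 30% of flow, odds ratio 1.0 to 4.0 per SD. A positive figure is a variance reduction and a negative one a loss.

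| Event rate | Expected events in 40 | Oxygen only | Oxygen plus three factors |
|---|---|---|---|
| 50% | 20 | 0% to +15% | −4% to +8% |
| 20% | 8 | −2% to +15% | −8% to +5% |
| 10% | 4 | −3% to +5% | −17% to −13% |

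In every setting the crude difference was within 0.005 of the truth on average.

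**The case against.** The strongest reply is that this is a descriptive proof-of-concept study, the crude difference is unbiased on average, and a shift of a few points is small beside an interval of about ±31. All of that stands, and it limits how much weight the point can bear.

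The SAP also has partial protections. Minimisation includes oxygen support. SAP 7.5 summarises the secondary endpoints by low- versus high-flow oxygen. SAP 6.3 tabulates baseline oxygen by arm, so an imbalance would be visible. Endpoint 6 analyses ventilation or death in a Cox model that may carry the stratification factors. None of these gives an adjusted risk difference. The subgroup splits on type of support rather than L/min, and endpoint 6 leaves baseline oxygen out. For endpoint 5 this last fact weakens the consistency argument, because its time-to-event counterpart is deliberately unadjusted for flow.

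Three stronger readings are tempting but not supported:

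- A reader might infer that the planned intervals under-cover. A simple Wald interval can fall slightly short at this size, but SAP 7.3 specifies exact or Wilson limits. A Wilson-based interval for the difference covered 96-97% in simulation under minimisation.
- A reader might apply the imbalance rate for simple 1:1 allocation, about 31%. The trial minimises on a factor related to oxygen, and that rate holds only if support type says nothing about flow.
- A reader might infer that precision is being lost for mortality as well. With about four deaths in 40, adjusting for oxygen gains almost nothing and the full covariate set loses 13-17%.

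**Conclusion.** The omission is real: no binary secondary endpoint has a covariate-adjusted contrast. For endpoint 2 this is out of line with the SAP's own handling of the AUC and endpoint 1. The consequence is chance error conditional on an imbalance in flow. It is neither systematic bias nor a fault in the planned intervals. Its size is modest, and the figures rest on an assumed success rate, an assumed prognostic strength and an assumed link between support type and flow. If flow is only weakly prognostic, adjustment changes little either way. The case for acting is that the change is nearly free and replaces a possible post hoc choice with a pre-specified one. The point is firm for endpoint 2, conditional for endpoint 5, and does not extend to mortality.

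**What to change.** In SAP 7.3:

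- **Endpoint 2.** Keep the crude difference with exact or Wilson limits. Pre-specify beside it a supportive standardised risk difference adjusted for baseline supplemental oxygen flow in L/min, from a logistic model with standardisation or a linear model with robust standard errors. Name one of the two.
- **Endpoint 5.** Do the same only if event numbers allow, and state the minimum count in advance. The calculations suggest that about eight events (20% of 40) can carry one covariate, while about four yield no useful gain.
- **Minimisation factors.** Add them only where events permit.
- **Mortality (endpoint 8).** Leave unadjusted.

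If the oxygen-support factor is to be a covariate, reconcile its definition first: high-flow nasal cannula (HFNC) is listed in SAP 3.4 but not in SAP 6.3 or protocol 17.2.

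The cost is a few lines of SAP text and one extra model per endpoint, using data already collected. The downside is little or no gain in precision if flow is weakly prognostic. If the blind has already been broken, the analysis belongs in the clinical study report, labelled post hoc.
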